3.6.3 Serious Adverse Event Reporting

Any serious adverse event will be reported to the IRB within one business day by telephone. The Chairman of the Institutional Review Board will be notified within one business day.

1. Subject's initials and subject number
2. Investigator's name
3. Protocol title and number
4. Subject's date of birth, gender, and race

5. LAP-BAND® System date of implantation surgery
6. Concomitant medication(s): dose, route, duration of treatment, date of last dose
7. Information regarding the adverse event:
 - description
 - date(s) the event began and ended
 - whether the experience resulted in death or was life-threatening
 - whether hospitalization was required or prolonged
 - any treatment(s) required
 - outcome(s) of treatment(s)
 - investigator's determination of relationship to the test article(s)

3.7 Data and Statistical Analysis

3.7.1 Primary Efficacy Variable

The primary efficacy variable is weight loss evaluated in terms of % excess weight loss (EWL).

3.7.2 Secondary Efficacy Variable(s)

The secondary variables for evaluation are:

- Body mass index (BMI)
- Status of co-morbidities
 - Diabetes Mellitus or Impaired Glucose Tolerance
 - Hypertension
 - Asthma
 - Obstructive sleep apnea
 - Dyslipidemia
 - Gastroesophageal reflux disease
 - Urinary stress incontinence
 - Depression
 - Osteoarthritis
 - Back pain
 - Dyspnea and respiratory abnormalities
- Quality of life scores, depression degree, psychiatric evaluation

In general, the status of the comorbid conditions will be classified as unchanged, improved, resolved, or worsened. For the analysis of change in comorbidity status by the McNemar test, unchanged or worsened will be grouped into one category and resolved or improved will be grouped into a second category. For diabetes, this means whether there is change in serum HbA1c, insulin, OGTT, or fasting serum glucose or the amount of medication or no need for medication,. For hypertension, this means whether there is change in blood pressure or the amount of medication or no need for medication. For asthma, this means whether there is change in the amount of medication or no need for medication. For sleep apnea, this means

whether there is change in the sleep apnea study or a normal sleep apnea study. For hyperlipidemia, this means whether there is change in the lipid panel or the amount of medication or no need for medication. For gastroesophageal reflux, this means whether there is change in an annual esophagram or their symptoms. For urinary stress incontinence, this means whether there is change in clinical symptoms. For depression, this means whether there is change in the amount of medication or no need for medication or specified psychiatric evaluations.

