3.4.5 Follow-Up Visits

3.4.5.1 Scheduled Visits

Study data will be collected at 1-2 week, 6 weeks, 3 months, 6 months, 9 months, 12 months, and every 6 months thereafter for a total of five years. Subjects will be weighed and given a physical examination. Parents and subjects will meet with the nutritionist at these same visits.

The subjects will maintain the behavior modification program worked out with the nutritionist and psychologist before surgery. These programs are individualized to each subject's dietary habits, eating habits, and quality of life issues. The subject will be encouraged and counseled to combine their Lap-Band tool with long-term modifications in their lifestyle, including exercise. Weight loss, status of pre-operative comorbidities and development of complications will be reviewed at every follow-up visit. This will include testing to follow pre-operative comorbidities. Baseline laboratory and nutritional parameters will be repeated every 3 months for the first year post op. OGTT will be performed at 1 year and 5 year on the subjects who have impaired glucose tolerance at baseline testing (excluding subjects who have type I or II diabetes who is not clinically safe to perform the test). However, if the HbA1c or fasting blood glucose tests show abnormal results or the subject develops polyuria or polydipsia, additional interval testing should be performed based on ADA guidelines.

All laboratory, gastrointestinal, EKG, nutritional, and psychiatric evaluations which were performed at baseline will be repeated every 12 months.

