3.7.6 Statistical Methods

Change in the primary efficacy endpoint, % EWL, will be evaluated by a linear modeling in which the covariance among repeated measures of weight loss from month 6 to month 60 is

modeled. SAS PROC MIXED will be used in which two covariance structures will be examined by means of a REPEATED statement: unstructured (UN) and autoregressive (AR(1)). AIC will be examined to determine the most suitable structure. In the case that AR(1) is selected, a RANDOM statement for Subject will be included in the model. The predictive variable of greatest interest in the model is time. % EWL is expected to increase after surgery, more quickly initially, and then more slowly. To test for this decelerating trend, Time will be log transformed. The residuals of the model will be examined, especially those relative to predicted weight loss over time to ensure that the model is not over or under predicting over the course of follow-up. Systematic departures of the residuals from the predicted time course may require adding a quadratic trend to the model or the choice of a different transformation for time. Covariates used in the model will include baseline weight (as measured by BMI).

The null hypothesis is that % EWL will remain unchanged (i.e., at zero) post surgery. The alternate hypothesis is that % EWL will be positive post surgery. An alpha of 0.05 will be used to determine if the null hypothesis is rejected. The form of the weight loss over time is not part of the hypothesis of the study, but instead is included to better understand the expected trend weight loss follows.

The secondary efficacy endpoint, BMI, will be tested using a model similar to that used to test % EWL. The covariance structure selected for the modeling of % EWL will be applied in the modeling of BMI. Similarly, the same transformation of time will be applied to this endpoint. Baseline BMI will not be included as a baseline covariate, but instead will be assigned a value of time 0 and will be included as an endpoint measure. The null hypothesis is that BMI will show no change from time of surgery. The alternate hypothesis is that BMI will decrease after surgery.

The secondary efficacy endpoint of change in co-morbidities will be examined by McNemar tests. The null hypothesis is that there is no change in each co-morbidity post surgery. The alternate hypothesis is that there will be a change in each co-morbidity.

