3.7.7 Data Collection

Data will be collected by the principal investigator, the nurse practitioner, or nutritionist and documented on a standardized data form. The data will be entered by a research coordinator or the principal investigator in a fashion that maintains patient anonymity, using a unique identification number. The data will be entered into a secure computerized database, which can be accessed only by the principal investigator and the research coordinator with the use of a password. Data collection and statistical analysis will be performed by assigned research personnel, who will access the data using the unique patient identification number assigned.

We will collect relevant life history information from the subject's medical records including illnesses and hospitalizations that occur while subjects are participating in the research, as well as age, ethnic background, marital status, medical history, weight loss, changes in weight-related medical conditions, and information about the surgery and information about lap-band adjustments, and complications. We will collect medical information from physicians and other healthcare providers in General Surgery, Pediatric Surgery, Pediatrics, Psychiatry, and Psychology and from the NYU hospital medical records.

All data will be recorded on case report forms and compared at 6, 12, 24, 36, 48, and 60 months with baseline. Results will be reported descriptively as well as by modeling weight loss in order to assess aggregate outcomes and address the issues of safety and efficacy.

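### The comorbidity McNemar test is applied to a change rating with no baseline value and pools worsened with unchanged, so on the closest reading worsening cannot affect the p-value

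*Combined protocol and SAP*

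**What the plan says.** Section 3.7.2 lists 11 comorbid conditions and states that in general "the status of the comorbid conditions will be classified as unchanged, improved, resolved, or worsened". For the McNemar test these four levels are reduced to two: "unchanged or worsened will be grouped into one category and resolved or improved will be grouped into a second category".

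Section 3.7.6 names the test: "The secondary efficacy endpoint of change in co-morbidities will be examined by McNemar tests". The hypotheses are "The null hypothesis is that there is no change in each co-morbidity post surgery" and "The alternate hypothesis is that there will be a change in each co-morbidity". The alternative has no direction.

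On timing, section 3.7.7 says "All data will be recorded on case report forms and compared at 6, 12, 24, 36, 48, and 60 months with baseline". None of the six times is named for the comorbidity test. No section defines a baseline value of the two-category variable or sets out the 2x2 table.

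**The concern.** McNemar's test compares one binary state measured twice in the same subjects. It uses only the two discordant cells: those who moved one way and those who moved the other. The variable in section 3.7.2 is itself a statement of change since baseline, so it has no value before surgery and there is nothing to pair it with. Pooling worsened with unchanged also removes the information that a test of change in either direction needs.

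At stake is what each of the 11 p-values means. It would answer whether enough subjects improved, not whether improvement outweighed worsening. A condition in which more subjects worsen than improve could be reported as a significant change, and one in which subjects only worsen would give no signal. Comorbidity status is part of the secondary objective (section 2.2), in a study without a control group. Worsening is also not far-fetched: section 3.4.5.2 names heartburn among the symptoms that prompt a band evaluation, and reflux, judged partly on symptoms, is one of the conditions tested.

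**Working it through.** **Inputs.** The rating, grouping, test and hypotheses come from sections 3.7.2 and 3.7.6. The 0.05 level is stated there for the %EWL hypothesis and is assumed to apply here. The alternative is read as two-sided. The plan gives no power, expected rate or number affected for this endpoint, so there is no figure to reproduce; all counts and rates below are assumptions. The version of the test is not stated, so exact and uncorrected chi-square results are both shown.

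**Possible readings of the table.**

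1. *Baseline coded not improved for everyone.* This is closest to the comparison with baseline in section 3.7.7. The discordant counts are b = number improved or resolved, and c = 0.
2. *The two groups treated as the discordant counts (improved share against 50%).* Worsened and unchanged still cannot be told apart: 10 improved of 40 gives p = 0.0022 whether 0, 10 or 30 of the rest worsened. If none of 40 changes, the split is 0 to 40 and the test rejects although nothing changed.
3. *Two postoperative visits compared.* This fits neither the null hypothesis in section 3.7.6 nor the comparison with baseline.
4. *Condition present or absent.* This would be a valid test, but an improved, unresolved condition is still present, and section 3.7.2 groups it with resolved.

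**Reading 1: improvers needed to reject.**

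- Exact: p = 2 × 0.5^b. b = 5 gives 0.0625; b = 6 gives 0.031.
- Uncorrected: chi-square = (b − c)²/(b + c) = b. b = 4 gives p = 0.046.
- Continuity-corrected: chi-square = (b − 1)²/b. b = 5 gives 3.20 (p = 0.074); b = 6 gives 4.17 (p = 0.041).

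The number worsened appears in none of these formulas. For a given number improved, the split of the rest between unchanged and worsened has no effect.

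**Illustration, 40 affected subjects (assumed).** p-values are exact, with uncorrected in brackets.

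| Improved | Worsened | Unchanged | Reading 1 | Improved v worsened |
|---|---|---|---|---|
| 8 | 12 | 20 | 0.008 (0.005) | 0.50 (0.37) |
| 2 | 14 | 24 | 0.50 (0.16) | 0.004 (0.003) |
| 0 | 12 | 28 | no discordant pair; p = 1 by convention | 0.0005 (0.0005) |

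For the first row, uncorrected: reading 1 has chi-square 8, while improved against worsened has (8 − 12)²/20 = 0.8.

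**Rejection rate with no net change (assumed: 20% improve, 20% worsen).** Under reading 1 this is P(Binomial(n, 0.2) ≥ 6) for the exact test and P(≥ 4) for the uncorrected one. For improved versus worsened it is a full trinomial enumeration.

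| Affected | Reading 1, exact (uncorrected) | Improved v worsened, exact (uncorrected) |
|---|---|---|
| 20 | 0.20 (0.59) | 0.02 (0.04) |
| 30 | 0.57 (0.88) | 0.02 (0.04) |
| 40 | 0.84 (0.97) | 0.03 (0.05) |
| 60 | 0.99 (1.00) | 0.03 (0.05) |

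**The case against.** The strongest reply is that the p-values attributed to the plan rest on a table that the plan never writes down. Section 3.7.2 mentions states that can be measured at both times, such as needing no medication or having a normal sleep study. The authors may have meant an ordinary before-and-after status test and described it badly. This stands as a doubt about intent, and the figures above hold only for the reading named. It does not rescue the text: the grouping sentence is explicit, it does not fit a present/absent table, and worsened stays merged with unchanged under the 50% reading as well.

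Second, the 20%/20% comparison is not a false-positive rate for the stated null. With 40% of subjects changing, a literal hypothesis of no change is false, and under reading 1 the test does not reject if nobody changes. That is correct. The comparison shows only that the test cannot tell net benefit from no net benefit. The case of none improved and 12 worsened shows the blindness without it.

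Third, the remedy depends on rating rules that are thin. Section 3.7.2 gives criteria for eight of the 11 conditions (none for osteoarthritis, back pain or dyspnea), and those eight refer to change without a threshold or a rule for conflicting measures. This stands too, but the planned four-level rating already needs such rules whichever test follows.

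Finally, the impact is bounded: the endpoint is secondary, and the four levels can still be reported descriptively.

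**Conclusion.** The concern holds and should be fixed. It rests on a stated rule, not merely on missing detail: section 3.7.2 assigns the McNemar test a post-surgery change rating, pools worsened with unchanged, and provides no baseline counterpart, while section 3.7.6 claims to test change without direction. On the reading closest to the text, six improvers (four without continuity correction) give significance however many others worsen, and worsening alone can never do so. That much is arithmetic, given a two-sided 0.05 level. How many of the 11 conditions would be affected depends on counts that the documents do not give. The primary %EWL analysis is untouched.

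**What to change.** Replace the grouping rule in section 3.7.2 and the matching sentences in section 3.7.6 as follows.

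- Analyse each comorbidity among subjects who had it before surgery. This matches section 3.4.5.1, where "status of pre-operative comorbidities and development of complications will be reviewed at every follow-up visit".
- Name one visit for the test. Table I marks comorbidities at 1 year and later but not at 3, 6 or 9 months, so a visit from 1 year on fits the schedule.
- Test improved or resolved against worsened with an exact sign (McNemar) test, treating unchanged as ties. Tabulate all four categories.
- Report new onset separately and descriptively.
- Where all subjects have the same assessment at baseline and follow-up, a present/absent McNemar table may be added.
- Write down, per condition, what counts as improved and worsened, including the three conditions that now have no criteria.

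The test itself needs only a change of wording, because the four-level rating is already planned; the rating rules take some further drafting. No new data are required.

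The price is significance that the current rule would give by construction. With 40% improving and 10% worsening (assumed), exact power for improved versus worsened is 0.37, 0.59, 0.74 and 0.91 at 20, 30, 40 and 60 affected (uncorrected 0.47, 0.67, 0.82, 0.94). Reading 1 would reject with probability 0.87, 0.99, 1.00 and 1.00 (exact) in the same case, because it ignores those who worsen.

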3.4.3 Baseline Evaluations

- Height and weight
- Blood pressure
- Baseline laboratory
 - Metabolic profile (Sodium, Potassium, Chloride, CO₂, BUN, Creatinine, Glucose, Calcium)
 - Hematologic profile (Hemogram)

- Thyroid panel (T₃, T₄, TSH, Free T₄)
- Lipid panel (Total cholesterol, LDL, HDL, Triglycerides)
- Hepatic function panel (Albumin, Alkaline Phosphatase, Total Bilirubin, Direct Bilirubin, ALT, AST, Total Protein)
- HbA1c and Insulin
- Nutritional panel (Iron, Folate, B12, Vitamin D 25-Hydroxy, PTH, Magnesium, Phosphorus)
- OGTT (Oral Glucose Tolerance Test) (excluding subjects who have Type I or II diabetes)
- Urinalysis
- Bone density
- Chest x-ray
- EKG
- Gall bladder ultrasound
- Serum pregnancy test (for female subjects)
- Pulmonary Function Testing (if indicated by history and physical)
- Sleep study (if indicated by history and physical)

Gastrointestinal evaluation will include:

- Esophagram
- Esophageal manometry, (if necessary, to evaluate for esophageal dysmotility if patient presents with dysphagia and abnormal esophagram indicating achalasia)

Nutritional evaluation will include:

- Initial nutritional assessment
- Follow up nutritional assessment

Psychiatric evaluation will be evaluated by:

- Psychiatric Assessment
- Child Behavior Checklist (parent and self-report, attached: Appendix C)
- Youth Evaluation Scale (parent and self-report, attached: Appendix D)
- Child Depression Inventory (CDI, attached: Appendix A)
- Three-Factor Eating Questionnaire (attached: Appendix B)
- SF-36 Health Survey (attached: Appendix E)

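### For dyslipidemia and diabetes, comorbidity status rests on change in several results with no size, direction or conflict rule, and the resulting label is not the paired state that McNemar needs.

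*Combined protocol and SAP*

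**What the plan says.** Section 3.7.2 sets the categories: "In general, the status of the comorbid conditions will be classified as unchanged, improved, resolved, or worsened". For the McNemar test, "unchanged or worsened will be grouped into one category and resolved or improved will be grouped into a second category".

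The criteria per condition follow. For dyslipidemia: "For hyperlipidemia, this means whether there is change in the lipid panel or the amount of medication or no need for medication". Section 3.4.3 shows that the panel is four results: "Lipid panel (Total cholesterol, LDL, HDL, Triglycerides". For glucose disorders: "For diabetes, this means whether there is change in serum HbA1c, insulin, OGTT, or fasting serum glucose or the amount of medication"; coming off medication altogether is listed as well. Section 3.4.5.1 limits one of those tests: "OGTT will be performed at 1 year and 5 year on the subjects who have impaired glucose tolerance at baseline testing". Section 3.4.3 also omits the baseline OGTT in subjects with type I or II diabetes.

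Other conditions have shorter lists. For hypertension: "For hypertension, this means whether there is change in blood pressure or the amount of medication or no need for medication". For asthma: "For asthma, this means whether there is change in the amount of medication or no need for medication". Sleep apnea rests on the sleep study and urinary stress incontinence on symptoms. Osteoarthritis, back pain and dyspnea are listed as endpoints without any criterion.

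Section 3.7.6 repeats that McNemar tests will be used, with a null hypothesis of no change in each comorbidity. Section 3.7.7 compares data with baseline at six time points (6, 12, 24, 36, 48 and 60 months). Neither section says which visit the comorbidity test uses.

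**The concern.** There are two problems.

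First, four continuous laboratory results will rarely all stay exactly the same, or all move in the same direction, between two visits. The criteria say which data are consulted but not how large a change counts, which direction counts, or what happens when LDL is better and triglycerides are worse. Two analysts following section 3.7.2 could label the same subject improved and worsened. The study is open-label with one arm, so whoever makes that choice knows the treatment and usually the weight loss.

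Second, McNemar compares the numbers of subjects who move in each direction between two binary states. Improved/resolved versus unchanged/worsened is one value per subject that already describes change. There is no second state to pair it with.

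Comorbidity status is part of the secondary objective in section 2.2 and is formally tested, so the tested share should not depend on an unstated choice.

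**Working it through.** The plan gives no rate, power or sample size for the comorbidity endpoint, so there is no figure to reproduce. The check asks what noise alone does to the stated criteria.

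**Inputs.** From the documents: k = 4 results for lipids (3.4.3); k = 4 tests for glucose disorders, or k = 3 without OGTT (3.7.2, 3.4.3, 3.4.5.1). Assumed: no true change, symmetric noise, equal correlation r between the components' changes, each signed so that positive is favourable, and no ties. The documents give no value for r, so a range is shown.

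**Formulas.** Let q be the probability that all k components move unfavourably. By symmetry it is also the probability that all move favourably.
- At least one better: 1 − q
- Both better and worse present: 1 − 2q
- Improved only if nothing worsened: q

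If the components are independent, q = 0.5^k. For k = 4, q = 0.0625, giving 1 − 0.0625 = 93.75% and 1 − 0.125 = 87.5%. At r = 0.5, q = 1/(k+1) = 0.20, giving 80% and 60%. The other correlations were simulated with 400,000 draws.

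| r (k = 4) | At least one better | Both better and worse | All better |
|---|---|---|---|
| 0 | 94% | 88% | 6% |
| 0.3 | 86% | 72% | 14% |
| 0.5 | 80% | 60% | 20% |
| 0.7 | 73% | 46% | 27% |
| 0.9 | 63% | 26% | 37% |

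The second and fourth columns bracket the share labelled improved. If any favourable result wins, it is 94% at r = 0 and 80% at r = 0.5. If any unfavourable result wins, it is 6% and 20%. The data are the same and only the unstated conflict rule differs. The share with conflicting results falls below half at r of about 0.65.

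**Three components (diabetes without OGTT).** Independent: 1 − 0.125 = 87.5% better and 1 − 0.25 = 75% both. At r = 0.5, q = 1/4, giving 75% and 50%.

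**Sensitivity for k = 4.** With total cholesterol tied arithmetically to LDL, HDL and triglycerides (illustrative levels and variation), the figures are 88% better and 76% both. With a tie probability t of 5% to 20% per component, independent, better is 1 − ((1+t)/2)^4, or 92% to 87%. Both is 1 − 2((1+t)/2)^4 + t^4, or 85% to 74%.

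**Other conditions.** Blood pressure, if systolic and diastolic are read separately (an assumption), has k = 2: 75% and 50% if independent, 67% and 33% at r = 0.5. Asthma, sleep apnea and incontinence each rest on one item, so conflict between tests cannot arise.

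**McNemar.** The statistic is (b − c)²/(b + c), where b counts subjects going from present to absent and c counts those going from absent to present. Section 3.7.2 supplies only the number improved or resolved and the number not. Neither b nor c can be read from these: someone improved may still have the condition, and someone unchanged may be in either state. If only subjects affected at baseline were used, c would be zero by construction.

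**The case against.** The strongest reply is that section 3.7.2 does not define improvement as any change in any test. It names four categories and lists the data to be consulted, leaving the judgement to the investigators. Two anchors exist: no longer needing medication, and a normal sleep study, both read naturally as resolved. This stands in part. The defect is a missing rule, not a stated bad one. But the anchors do not separate improved from worsened when laboratory results disagree, and nothing in sections 3.4.3, 3.4.5.1 or 3.7.6 fills the gap.

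A reader might infer that the endpoint is biased towards benefit. The documents do not support that. The model is symmetric, and if an unfavourable result takes precedence the same noise pushes subjects into unchanged or worsened. Only indeterminacy is shown.

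A reader might also infer that most of the up to 120 subjects are affected. That does not follow either. The percentages apply only to subjects with a lipid or glucose disorder at baseline, a number the documents do not give. They do not carry over to blood pressure at the same size, or to the single-item conditions. Most diabetes assessments have three tests rather than four, and high correlation between components weakens the effect. The primary endpoint, % EWL, is untouched.

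**Conclusion.** The concern holds for dyslipidemia and for diabetes or impaired glucose tolerance. Status cannot be assigned reproducibly from section 3.7.2, and noise can decide it. With four components and assumed correlation of 0 to 0.5, 60% to 88% of affected subjects with no true change would have conflicting results; at correlation 0.7 to 0.9 it is 46% to 26%. These figures illustrate the mechanism and do not predict this trial's results. They rest on symmetric noise and equal correlation, neither of which the documents give.

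The mismatch with McNemar is separate and needs no assumption: it follows from the definition of the label and affects every comorbidity. Together the two points make this a change the sponsor should make, for a secondary endpoint.

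**What to change.** In section 3.7.2, score each comorbidity that has collected data as present or absent at baseline and at one fixed primary visit. Use one criterion per condition, named by the sponsor before analysis: on medication, or beyond the cut-off of one named measure. Include all subjects assessed at both times, not only those affected at baseline, and run McNemar on those paired states. For tests done only if indicated, such as the sleep study, state that the result applies to those tested at both times.

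Report improved and worsened descriptively, on the one named measure, and only when the change exceeds repeat-test variation. As an illustration, a threshold of 1.96 SD of the test-retest difference labels 2.5% improved by noise on one named measure, against 1 − 0.975^4 = 9.6% if any of four independent measures may count. It would not help to require that no other component moves the other way: with three other independent components only 0.5^3 = 12.5% of subjects would meet that by chance, so noise would remove most genuine improvers.

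The sponsor must state the diabetes criterion itself. Section 3.4.5.1 refers to ADA guidelines only for additional testing and does not adopt them as an outcome definition. Report osteoarthritis, back pain and dyspnea descriptively, since they have no criterion.

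The cost is plan wording and recoding of mostly collected data. The downside is that fewer subjects will be labelled improved, and partial improvement will not enter the test.

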3.4.5.2 Band Adjustments

Fluid will be added to or removed from the band as indicated by the clinical progress, physical examination, and esophagram done at follow-up visit.

The adjustments will be performed as per study device manufacture's DFU.

Visits for band adjustments can also be initiated by the patient or their course between scheduled visits. If they lose weight too quickly; develop symptoms such as heartburn, nausea, vomiting or overeating; or develop a condition or illness requiring them to eat more, they will be evaluated for removal of fluid from the band. If they lose weight too slowly or overeat, they will be evaluated for addition of fluid to the band. Each evaluation will involve review of their clinical progress, physical examination, and esophagram if necessary.

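### The reflux status rule leaves out acid-suppressing medication, so it can misclassify subjects as improved or as unchanged

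*Combined protocol and SAP*

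**What the plan says.** Section 3.7.2 lists gastroesophageal reflux disease among eleven comorbidities whose status is a secondary efficacy variable. Each is to be called unchanged, improved, resolved or worsened. The reflux rule is: "For gastroesophageal reflux, this means whether there is change in an annual esophagram or their symptoms".

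The neighbouring rules bring in treatment. For example, "For hypertension, this means whether there is change in blood pressure or the amount of medication or no need for medication", and "For asthma, this means whether there is change in the amount of medication or no need for medication". Diabetes, hyperlipidemia and depression are handled in the same way.

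For the test, "unchanged or worsened will be grouped into one category and resolved or improved will be grouped into a second category". Section 3.7.6 adds: "The secondary efficacy endpoint of change in co-morbidities will be examined by McNemar tests".

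The only concomitant drugs that the protocol restricts are chronic aspirin or NSAIDs and weight-loss drugs (3.2.2, 3.4.6). Acid suppressants are not mentioned anywhere. Table I records comorbidities and concomitant medications in one row, at screening, at year 1 and every six months after that.

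**The concern.** Being free of reflux symptoms means different things with and without treatment. A rule that looks at symptoms or the esophagram, but not at the drugs taken, cannot tell a subject whose reflux went away after banding from one whose reflux is controlled by a new prescription. The trial has no control arm, so no comparison elsewhere in the design separates the two.

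The same blind spot hides real benefit. A subject who was controlled on acid suppression before surgery and no longer needs it shows no change in symptoms and gets no credit.

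At stake is the reflux improvement rate and its McNemar test. The protocol expects heartburn after banding: 3.4.5.2 lists it among the symptoms that lead to evaluation for fluid removal ("develop symptoms such as heartburn, nausea, vomiting or overeating"). Treatment for reflux during follow-up is therefore foreseeable.

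**Working it through.** The documents give no reflux prevalence, expected rate or power, so there is no planned figure to reproduce. The check has two parts.

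**1. Applying the rule to three subjects, all with reflux at baseline**

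| Subject | Baseline | Annual visit | Class as written | Class with medication considered |
|---|---|---|---|---|
| A | symptoms, no drug | no symptoms, no drug | improved/resolved | improved/resolved |
| B | symptoms, no drug | no symptoms, new acid suppressant | improved/resolved | not improved |
| C | no symptoms, on acid suppressant | no symptoms, drug stopped | unchanged | improved/resolved |

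The esophagram is taken as unchanged throughout. Because esophagram and symptoms are joined as alternatives, the symptom change alone is enough for B. If *a* subjects are like B and *s* are like C, the counted number improved is the true number + *a* − *s*. The documents give neither *a* nor *s*.

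**2. How many errors matter**

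Inputs: the grouping in 3.7.2; the McNemar test in 3.7.6; a two-sided test, read from "The alternate hypothesis is that there will be a change in each co-morbidity"; and 0.05, which 3.7.6 states only in the %EWL paragraph ("An alpha of 0.05 will be used to determine if the null hypothesis is rejected"). The maximum sample is 120 (3.1).

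With *k* subjects changing in one direction and none in the other, the exact two-sided p = 2 × 0.5^k:

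- k = 4: 0.125
- k = 5: 0.063
- k = 6: 0.031
- k = 7: 0.016

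Towards benefit: six subjects like B, with no other change, give p = 0.031. Away from benefit: if six subjects truly improve but two of them are like C, four are counted and p moves from 0.031 to 0.125.

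Assumed baseline prevalence of 10%, 20% or 30% of 120 gives 12, 24 or 36 reflux subjects. Six is then 6/12 = 50%, 6/24 = 25% or 6/36 = 17% of them.

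**Illustration of the upward direction only.** Assume 24 reflux subjects, no effect of banding, 15% improving spontaneously, and a fraction *f* of the rest made symptom-free by a new drug. The counted share improved is 0.15 + 0.85*f*: 15% at f = 0, 23.5% at f = 0.1, 32% at f = 0.2 and 40.5% at f = 0.3.

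- Under the grouping in 3.7.2, applied to baseline cases, worsened subjects supply no opposing pair. Significance then needs six or more improved. P(X ≥ 6) with X ~ Binomial(24, 0.15 + 0.85*f*) is 14% at f = 0, 51% at f = 0.1 and 83% at f = 0.2.
- If improved is instead set against worsened, with 15% also worsening spontaneously, the chance of a significant improvement is about 1% at f = 0, 6% at f = 0.1, 21% at f = 0.2 and 45% at f = 0.3.

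The 14% at f = 0 comes from the grouping and not from the reflux rule. Only the rise from there belongs to this point. Subjects like C would pull the other way and are not in this illustration.

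**The case against.** The strongest reply is that the paragraph opens in general terms and lists where to look for change; it is not a scoring algorithm. Table I puts comorbidities and medications in one row, so an assessor has both in view. That is fair as a description of practice. However, the reflux sentence names its two criteria and medication is not one of them, while five neighbouring rules do name it. An assessor who follows the text has no ground to use it.

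A second reply is that the other rules join outcome and medication as alternatives with no order of priority, so lower blood pressure on a new drug could also be called improved. Sleep apnea and stress incontinence have no medication term either. This stands. It means that copying the hypertension wording would not cure the reflux rule; an explicit priority is needed.

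Three stronger readings are tempting, and the documents do not support them:

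- *The omission biases the result towards benefit.* Subject C shows the opposite error, and nothing in the documents says how many baseline cases take acid suppressants.
- *A subject whose band was loosened for heartburn should not count as improved.* Adjustment is part of the device therapy (1.1, 3.4.5.2). Fluid removal mainly relieves symptoms that the band itself caused, and the subject must still be better than before surgery to count as improved.
- *The rule hides harm from the device.* Adverse events are recorded and evaluated at each visit (3.6, Table I), and annual esophagrams are a safety evaluation (3.7.5). Harm has other routes into the record.

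**Conclusion.** The point holds as a two-way misclassification. As written, the reflux rule counts a subject made symptom-free by new or increased acid suppression as improved, and counts a subject who stops the drug and stays well as unchanged. The net direction cannot be known from the documents.

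The size is conditional. About six net errors in one direction can be enough to produce a nominally significant result, and a loss of two can remove one. The count of six, the 10% to 30% prevalence and the 15% spontaneous rates are assumptions for illustration. The p-values also assume an exact two-sided test at 0.05.

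The reach is limited to one of eleven comorbidities within a secondary endpoint. The primary %EWL analysis is untouched. The rule should still be corrected, because it is a stated rule that can give a wrong answer and the data to correct it are already planned.

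**What to change.** In 3.7.2, replace the reflux sentence with a rule that classifies status at annual visits jointly from symptoms, esophagram and acid-suppressing medication, each relative to baseline:

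- Improved or resolved requires either a favourable change in symptoms or esophagram with acid suppression no higher than at baseline, or reduced or stopped acid suppression with symptoms and esophagram no worse.
- A subject with new or increased acid suppression is not classed as improved.
- Band fluid removal for reflux symptoms is reported descriptively beside the status and does not change it.

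The same sentence should say which finding prevails when symptoms and esophagram disagree, which the present wording leaves open.

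Apply the rule from year 1. Table I has no concomitant-medication entry at month 6, although 3.7.7 compares data with baseline at that time.

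This changes how an outcome is classified, not how subjects are treated. The cost is a short text change and a cross-check against medication and adjustment records that are already collected. The reflux improvement rate may move slightly in either direction.
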